### Assessments of fertility

Refer to Section 5.2 for criteria to determine women that are not of childbearing potential.

Medical documentation of oophorectomy, hysterectomy, or tubal ligation must be retained as source documents. Subsequent hormone level assessment to confirm the woman is not of childbearing potential must also be available as source documentation in the following cases:

- 1. Surgical bilateral oophorectomy without a hysterectomy.
- 2. Reported 12 months of natural (spontaneous) amenorrhea with an appropriate clinical profile.

In the absence of the above medical documentation, FSH testing is required of any female patient who states that they are of non-childbearing potential regardless of reported reproductive/menopausal status at Screening/Baseline.

### 8.4.3 Other safety evaluations

A standard 12-lead electrocardiogram (ECG) will be performed as indicated in Table 8-1 and will be reviewed locally. Clinically relevant abnormalities should be recorded on the relevant medical history/current medical conditions/AE eCRF page for the Screening ECG.

### 8.4.4 Appropriateness of safety measurements

The safety assessments selected are standard for this indication/patient population as well as for secukinumab clinical studies.

### 8.5 Additional assessments

### 8.5.1 Thyroid eye disease quality of life

Quality of life will be evaluated with the use of the GO-QoL questionnaire, comprising 2 subscales assessed separately or in combination (Terwee et al 1998). These 2 subscales are as follows:

1. The consequences of double vision (diplopia) and decreased visual acuity on visual functioning, and

2. The psychological consequences of a changed appearance.

Scores on each sub-scale as well as the score on the overall GO-QoL scale have a range of 0 to 100 points. A change of 8 points is considered to be clinically relevant.

### Guidelines for administering GO-QoL questionnaire

The patient must be given the GO-QoL questionnaire at the scheduled visit before any clinical assessments are conducted. A patient's refusal to complete all or any part of a questionnaire should be documented in the study data capture system and should not be captured as a protocol deviation. Handling of protocol deviations can be modified if needed per study protocol.

The GO-QoL questionnaire should be completed in the language most familiar to the patient.

[figure not shown]
If self-administered, the patient should be given sufficient space and time to complete the questionnaire.

[figure not shown]
The site personnel should check the GO-QoL for completeness and ask the patient to complete any missing responses. The questionnaire will be completed on paper. This will be considered the source file.

Completed measure(s) (including when using paper questionnaire measures and any unsolicited comments written by the patient) must be reviewed and assessed by the investigator for responses, which may indicate potential AEs or SAEs before any clinical study examinations. This assessment should be documented in study source records. If AEs or SAEs are confirmed, study investigators should not encourage the patient to change responses reported in the completed questionnaires. Study investigators must follow reporting instructions outlined in Section 10 of the study protocol.

In the event of a major healthcare disruption (e.g., a pandemic or epidemic) that limits or prevents on-site visits to the study site the GO-QoL might alternatively be done remotely from the patient's home (e.g., online), depending on local regulations and technical capabilities.

# 9 Study discontinuation and completion

# 9.1 Discontinuation and completion

# 9.1.1 Study treatment discontinuation and study discontinuation

The investigator closely monitors the disease activity of a patient throughout the entire study and must discontinue study treatment or study participation for a given patient if he/she believes that continuation would negatively impact the patient's well-being.

Discontinuation of study treatment for a patient occurs when study treatment is stopped earlier than the protocol planned duration and can be initiated by either the patient or the investigator.

Study treatment must be discontinued under the following circumstances:

- Subject decision.
- If any of the following (evidence of disease progression) occurs in the study eye or fellow (contralateral) eye:
  - Compressive optic neuropathy that in the opinion of the investigator requires urgent surgical intervention or medical treatment with glucocorticoids
  - Severe corneal injury that requires surgical treatment
  - Severe/major loss of vision defined as a decrease of best-corrected visual acuity to below 0.1 (Snellen equivalent of 20/200)
  - Other abnormalities not here specified but that the investigator determines would require study treatment discontinuation
- Emergence of the following AEs:
  - Any severe or SAE that is not compatible with administration of study medication, including AEs that require treatment with an unacceptable concomitant medication.

- Onset of lymphoproliferative disease or any malignancy, except for treated basal cell carcinoma, treated actinic keratoses, treated *in situ* carcinoma of the cervix or non--invasive malignant colon polyps which are being or have been removed.
- Life-threatening infection.
- Severe hypersensitivity reaction or anaphylactic reaction.
- Any laboratory abnormalities that in the judgment of the investigator are clinically significant and are deemed to place the patient at a safety risk for continuation in the study (a general guidance on clinically notable laboratory values is provided in Appendix 1).
- Pregnancy.
- Use of any biologic immunomodulating agent except secukinumab.
- Other treatment or procedure for TED in case of worsening of the disease.
- Any protocol deviation that results in a significant risk to the patient's safety.
- Use of prohibited treatment as per recommendations in the prohibited treatment section if the treatment with prohibited medication increases the patient's safety risk and if it cannot be discontinued.
- Emergency unblinding

If discontinuation of study treatment occurs, the investigator should make a reasonable effort to understand the primary reason for the patient's premature discontinuation of study treatment and record this information.

In addition to the study treatment discontinuation criteria above, which apply throughout the entire study, the following criterion applies from week 16 onwards for discontinuation of study participation of a patient:

Any deterioration compared to baseline values that the investigator considers to be clinically relevant in this individual case will result in study discontinuation of the patient. The evaluation should take into account the overall course of the disease of the individual case (e.g., individual fluctuations of ocular parameters).

Patients may decide to discontinue their participation in the study for any reason at any time.

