	For patients not receiving open-label secukinumab treatment a follow-up visit 8 weeks after Week 16 visit should be scheduled, if not yet completed. At this follow-up Visit, the assessments associated with visit Week 24 (for responder) should be performed.
	Definitions of proptosis responder, non-responder and relapser
	Proptosis responder : Patients achieving response in reduction of proptosis at Week 16 defined as follows: reduction of $\ge 2$ mm from Baseline in the study eye without deterioration ( $\ge 2$ mm increase) of proptosis in the fellow eye.
	Proptosis non-responder : Patients not achieving response in reduction of proptosis at Week 16 with "response" defined as follows: reduction of $\ge 2 \text{ mm}$ from Baseline in the study eye without deterioration ( $\ge 2 \text{ mm}$ increase) of proptosis in the fellow eye.
	Proptosis relapser : Patients who are "proptosis responders" as defined above, and then relapse based on proptosis with relapse defined as follows: increase in proptosis of ≥ 2 mm compared to Week 16 in the study eye or deterioration of proptosis (≥ 2 mm increase) in the fellow eye at any time during 52-week follow-up period.
	In case of worsening of the disease, patients may receive alternative treatment for TED at the discretion of the investigator and will be discontinued from the study treatment.
	The primary endpoint analysis will be performed as an interim analysis once all patients have reached Week 40, which will include the primary efficacy endpoint (Week 16), efficacy of retreatment for initial non-responders and during 24 weeks of follow-up. The final analysis will be performed when the last patient has reached the end of trial. Other interim analyses may be performed in accordance with HA requirements.
Population	Male or female patients with active, moderate to severe TED.

	1
Key inclusion criteria	
 
Patient must be able to understand and communicate with the investigator and comply with the requirements of the study and must give a written, signed and dated informed consent before any study assessment is performed.
 
Male or non-pregnant, non-lactating female patients ≥ 18 years of age.
 

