### Definitions of proptosis responder, non-responder and relapser

**Proptosis responder:** Patients achieving response in reduction of proptosis at Week 16 defined as follows: reduction of  $\geq 2$  mm from Baseline in the study eye without deterioration ( $\geq 2$  mm increase) of proptosis in the fellow eye.

[figure not shown]
**Proptosis non-responder:** Patients not achieving response in reduction of proptosis at Week 16 with "response" defined as follows: reduction of  $\ge 2$  mm from Baseline in the study eye without deterioration ( $\ge 2$  mm increase) of proptosis in the fellow eye.

**Proptosis relapser:** Patient who are "proptosis responders" as defined above, and then relapse based on proptosis with relapse defined as follows: increase in proptosis of  $\geq 2$  mm compared to Week 16 in the study eye or deterioration of proptosis ( $\geq 2$  mm increase) in the fellow eye at any time during 52-week follow-up period.

In case of worsening of the disease during study treatment, patients may receive alternative treatment for TED at the discretion of the investigator and will be discontinued from the study treatment (please refer to Sections 6.2.3 and 9.1.1).

The maximum duration of the study is 108 weeks: 16 weeks (initial treatment phase) + 52 weeks (follow-up) + 16 weeks (second treatment cycle) + 24 weeks (second follow-up period).

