#### Figure 3-1 Study design

# 4 Rationale

# 4.1 Rationale for study design

This study consists of a 16-week double-blind treatment period during which the efficacy and safety of secukinumab 300 mg s.c. for the treatment of patients with moderate to severe TED will be evaluated in a placebo-controlled manner, and a 52-week follow-up period. In addition, it offers a course of open-label secukinumab for participants who fail to respond to treatment at Week 16 (second course for those who received secukinumab initially and first course for those who received placebo initially), and a course of secukinumab for patients who respond at Week 16 but subsequently relapse. Following the course of open-label secukinumab there is a subsequent 24-week follow-up period.

The **randomized design** (including stratification for smoking, a key modifier of TED disease severity and response to immunosuppressive treatment of TED [Eckstein et al 2003]) ensures a comparable and balanced patient profile across treatment arms. The **placebo-controlled**, **double-blind design** allows the assessment of the efficacy and safety of secukinumab 300 mg in comparison to placebo in an adequate setting.

In case of relapse during the follow-up period, patients will be offered the option for re-treatment with open-label secukinumab 300 mg for 16 weeks (including 5 secukinumab injections during the first 5 weeks). This enables collection of data on the efficacy and safety of re-treatment in case of relapse.

Furthermore, the trial offers proptosis non-responders at Week 16 the option of a course of open-label secukinumab 300 mg s.c. (administered as above for relapsers). This will allow exploration of whether an extended treatment period could be beneficial for patients who have not achieved a sufficient response after 16 weeks of treatment. This continued treatment option will be offered to patients from both treatment arms, active as well as placebo. Since a very low rate of response under placebo treatment can be expected, this study design enables placebo treated patients to also receive a course of active treatment within this clinical trial (in case they have not achieved response at Week 16). In addition, if placebo-treated patients achieve a response and relapse (unlikely scenario), they will be offered a course of open label secukinumab.

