### Premature discontinuation of study treatment

Patients who prematurely discontinue study treatment during the double-blind treatment period (Weeks 0 - 16) or during a course of open-label secukinumab administered during the followup period (at or after Week 16), for any reason other than withdrawal of informed consent should **not** be considered as discontinued from the study. **Where possible, they should return for the study visits indicated** in the Assessment Schedule during treatment. These include up to Week 16 (if discontinued during double-blind treatment), up to NR32 (for non-responders), and up to R16 (for relapsers). In case patients are not willing to continue attending further study visits, they should attend an End of Treatment (EOT) visit 4 weeks after the last dose of study drug. This EOT visit includes all assessments of the Week 16 (if discontinued during doubleblind treatment), NR32 (for non-responders) or R16 (for relapsers) visit. Additionally, a follow-up visit (EOS) should be done 12 weeks after last study drug administration, including all assessments done at: Week 24 (if discontinued during double-blind treatment), Week NR40 (for non-responders) or Week R24 (for relapsers).

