### Premature discontinuation of study

Participants who prematurely discontinue the study for any reason should be scheduled for a visit as soon as possible, at which time all of the assessments listed for the study discontinuation visit will be performed. This study discontinuation visit should include all assessments of the Week 16 (if discontinued during double-blind treatment), NR32 (for non-responders), R16 (for relapsers) or Week 68 (for patients who discontinued during the follow-up period) visit.

Additionally, all randomized and/or treated patients should have a follow-up (EOS) visit conducted 12 weeks after last administration of study treatment, if not yet completed (or at least a safety follow-up call or contact, if a visit cannot be performed). This EOS visit includes all assessments of the Week 24 (if discontinued during the double-blind treatment period or the follow-up for responders), Week NR40 (for non-responders) or Week R24 (for relapsers) visit. The information collected is recorded in the eCRF. Documentation of attempts to contact the patient should be recorded in the source documentation.

For all premature discontinuations noted above, if the patient fails to return for these assessments for unknown reasons, every effort (e.g., telephone, e-mail, letter) should be made to contact the participant/pre-designated contact as specified in the lost to follow-up section. This contact should preferably be done according to the study visit schedule.

If the patient cannot or is unwilling to attend any visit(s), the site staff should maintain regular telephone contact with the patient, or with a person pre-designated by the patient. This telephone contact should preferably be done according to the study visit schedule.

After study treatment discontinuation or study discontinuation, at a minimum, in abbreviated visits, the following data should be collected at clinic visits or via telephone/email contact:

- New/concomitant treatments
- AEs/SAEs

The investigator must also contact the IRT to register the patient's discontinuation from study treatment.

If discontinuation occurs because treatment code has been broken, please refer to Emergency breaking of treatment code section.

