# 12 Data analysis and statistical methods

The data will be analyzed by Novartis and/or a designated CRO.

The primary endpoint analysis will include the primary endpoint (Week 16) and results of retreatment for proptosis non-responders, after all patients have completed the Week 40 visit assessment. This will support potential regulatory filing as described in Section 4.4. A final analysis is planned at the EOS once all patients have completed their EOS visit. There may be analyses in addition to Week 40 and Week 108 timepoints to support regulatory filings.

Any data analysis carried out independently by the investigator should be submitted to Novartis before publication or presentation.

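### From Week 16, clinically relevant deterioration ends study participation rather than only study treatment, so by-visit retreatment results can look somewhat too favourable

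*Protocol*

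**What the plan says.** **Leaving the study.** Protocol Section 9.1.1 first lists reasons to stop study treatment, among them sight-threatening progression in either eye and other TED treatment for worsening. It then adds a separate criterion for ending study participation from Week 16: "Any deterioration compared to baseline values that the investigator considers to be clinically relevant in this individual case will result in study discontinuation". The investigator judges this against the patient's overall course.

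**Stopping drug only.** Under the paragraph on premature discontinuation of study treatment, patients who stop double-blind or open-label drug "for any reason other than withdrawal of informed consent" are not study discontinuations. Where possible they keep attending, to NR32 for non-responders and R16 for relapsers. Those unwilling to do so get an EOT visit 4 weeks and an EOS visit 12 weeks after the last dose. Section 3 similarly says that when disease worsens during study treatment, "patients may receive alternative treatment for TED at the discretion of the investigator and will be discontinued from the study treatment".

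**What a leaver still provides.** Under premature discontinuation of study, a visit is due as soon as possible with all NR32 or R16 assessments. An EOS visit with all NR40 or R24 assessments follows 12 weeks after the last dose, "or at least a safety follow-up call or contact, if a visit cannot be performed".

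**Purpose of the open-label course.** Section 4.1 wants "exploration of whether an extended treatment period could be beneficial for patients who have not achieved a sufficient response". The Protocol summary includes in the Week 40 analysis "efficacy of retreatment for initial non-responders and during 24 weeks of follow-up", and Section 12 includes "results of retreatment for proptosis non-responders". Table 8-2 puts a second responder assessment at NR32/R16.

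**SAP.** Secondary endpoints are summarised descriptively by visit (2.6.2), missing values are not replaced (2.6.3), and percentages generally leave missing values out (2.1). Table 2-2 keeps windows for the NR visits. Reasons for study discontinuation are tabulated in the disposition summary (2.3.1). Exploratory endpoints are dropped (2.7).

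**The concern.** The exit is triggered by the outcome being measured. If patients who worsen on the open-label course leave, and later visits are summarised on whoever attended, each later summary rests increasingly on patients who did not worsen. The direction is favourable to retreatment. What is at stake is the answer to the Section 4.1 question of whether a further course helps Week 16 non-responders.

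The protocol handles Week 16 differently. Section 2.1 uses the response status retrieved after treatment discontinuation and counts other TED treatment for worsening as non-response. Section 6.2.2 also classes patients who use other TED treatment during study treatment as non-responders. The visible text of the amended SAP carries no such rule past Week 16.

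**Working it through.** The plan gives no figure for this loss, so the check has two parts: which visits can go missing, and what a missing value does to a percentage.

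**1. Inputs.** Protocol Table 8-2 target days: NR16 113, NR17 120, NR18 127, NR19 134, NR20 141, NR24 169, NR28 197, NR32 225, NR40 281. CAS, proptosis, diplopia and GO-QoL are assessed at NR16, NR18, NR20, NR24, NR28, NR32, NR40 and NR56. SAP Table 2-2 windows: NR24 156-183, NR28 184-211, NR32 212-253, NR40 254-337. The SAP 2.1.1.2 formula for assessments not scheduled at every visit ends NR18 at int((127+141)/2) = 134, so NR20 runs from Day 135 to 155 for these measures (Table 2-2 prints 138-155).

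**2. Visits lost.** EOS day = last dose day + 84. Assume dosing on schedule, worsening found before that day's dose, and the discontinuation visit held on the exit day. Only efficacy visits after exit and up to NR32 are counted.

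| Exit at | Last dose day | EOS day (window) | Empty if EOS is a visit | Empty if EOS is a call |
|---|---|---|---|---|
| NR18 | 120 | 204 (NR28) | NR20, NR24, NR32: 3 of 4 | 4 of 4 |
| NR20 | 134 | 218 (NR32) | NR24, NR28: 2 of 3 | 3 of 3 |
| NR24 | 141 | 225 (NR32) | NR28: 1 of 2 | 2 of 2 |
| NR28 | 169 | 253 (NR32, last day) | none: 0 of 1 | 1 of 1 |

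Variations:

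- If the patient is dosed on the exit day, EOS falls on Day 211, 225 or 253 for exit at NR18, NR20 or NR24, and the same visits are empty. For exit at NR28 it moves to 197 + 84 = 281 (NR40), so NR32 is empty.
- For exit at NR28 before dosing, an EOS visit one day late also maps to NR40.
- The discontinuation visit need not fall on the exit day. After an NR18 exit, holding it on Days 135-155 fills NR20, leaving 2 of 4 empty with an EOS visit and 3 of 4 with a call.
- If the patient only stops drug and attends as Section 9.1.1 asks, none of these visits is empty. That is a best case, because attendance is required only where possible.

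**3. Effect on a percentage.** With x improved among n patients, dropping one unimproved patient changes x/n to x/(n-1), a factor of n/(n-1).

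- Terminated study: SAP Section 1 has 23 patients entering follow-up, so n is at most 23 and the factor is at least 23/22 = 1.045.
- Planned study: 35 per arm at 60% versus 20% (Section 12.8.1; the 35 reproduces with the continuity-corrected formula at 90% power). Expected non-responders are 35 x 0.40 + 35 x 0.80 = 14 + 28 = 42, giving 42/41 = 1.024. This assumes that the rates hold for proptosis and that all accept the offer.
- Illustration, with all 23 retreated and 6 counted as improved (both assumed): the rate with leavers counted is 6/23 = 26.1%. With 1, 2, 3 or 5 leavers lacking a value, the observed-case rate is 6/22 = 27.3%, 6/21 = 28.6%, 6/20 = 30.0% or 6/18 = 33.3%.

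If x = 0 the percentage stays at 0. SAP Section 1.2 reports no responders, so a responder row may not move at all in the terminated study. Means and other non-zero percentages could.

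**The case against.** The strongest reply is that little of consequence is exposed. Every primary and secondary efficacy endpoint is at Week 16, and the rule starts there. The open-label data are uncontrolled and descriptive. The SAP specifies no post-Week 16 efficacy percentage table, and its NR windows also serve laboratory tests, vital signs and dose counts. Part of the protocol is blacked out, so a rule for retreatment dropouts may exist unseen. The worsened value is recorded at exit, and the reason for leaving appears in the disposition summary. Exit on the investigator's judgement of patient welfare is a deliberate additional rule, and Section 3 has a different trigger, the start of other TED treatment.

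Most of this stands and limits the point to a small one. It does not remove it. Welfare is already protected by stopping drug and allowing other therapy, which Sections 4.5 and 6.2.3 permit, so ending visits as well adds no protection.

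Three stronger readings might be inferred, and the documents support none of them:

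- *That the worsening goes unrecorded.* The discontinuation visit captures it, and an attended EOS visit often fills NR32.
- *That the documents fix exactly which visits are lost.* The counts depend on when the discontinuation visit is held and whether EOS is attended.
- *That deterioration exits can be counted from the existing disposition reasons.* The documents do not list those reasons, so these exits may not be separable.

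**Conclusion.** The point holds as a cheap improvement of small and unknown size. Section 9.1.1 creates an outcome-driven exit from Week 16 that sits awkwardly beside its own follow-up rule for patients who stop open-label drug. With observed-case summaries by visit, it tilts any retreatment results in the favourable direction. The likely loss is some visits between exit and NR32, mainly NR20 to NR28, and NR32 too if EOS is only a call or falls outside that window.

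This rests on on-schedule dosing, on efficacy summaries being produced after Week 16, and on at least some patients leaving for deterioration; no count is given. The relapser branch is probably empty, since the SAP reports no responders and gives no relapser windows. Sponsor termination is a separate cause of missing later visits.

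A reader might infer that the trial's efficacy conclusion is affected. It is not: the Week 16 endpoints are untouched, and no efficacy endpoint listed in the SAP lies later.

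**What to change.** 1. **Section 9.1.1, patients on an open-label course.** State that clinically relevant deterioration stops study treatment, with visits continued to NR32/R16 under the existing follow-up rule where the patient agrees.
2. **Section 9.1.1, patients not on drug** (responders in follow-up, or patients after their last retreatment dose). They have no study treatment to stop, so state that they may receive other TED therapy and continue scheduled visits if willing.
3. **Any retreatment response summary.** Count patients who deteriorate or start other TED therapy as non-responders. For other TED therapy this is what Section 2.1 already does at Week 16.
4. **Terminated study.** If post-Week 16 efficacy summaries are produced, report with them the number of exits for deterioration, where the recorded reason allows it.

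Cost: a short change to Section 9.1.1 and one reported count. For a patient whose worsening is found at NR18 or later in the open-label course, it means at most four further efficacy visits (NR20, NR24, NR28, NR32), all already in Table 8-2, some of them on other TED therapy. Patients remain free to leave. Items 1 and 2 can no longer change data in the terminated study; items 3 and 4 need only what was recorded.
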